13.2.5 Reporting of Serious Adverse Events

Reporting requirements for SAEs will be managed on behalf of the Sponsor by the CRO. Full details of the procedures to be adopted will be documented in a safety management plan approved by responsible parties, in brief:

The Investigator will report any SAE that occurs to any patient from the time written informed consent is signed through the last visit. If an SAE occurs after informed consent and is resolved before the first dose of investigational drug in RPC01-3102, the event will be captured in the parent trial only (eg, RPC01-3101 or RPC01-202). If the SAE is ongoing at the time of the first dose in RPC01-3102, it will be transcribed into the eCRF for RPC01-3102. If an SAE occurs after the first dose of investigational drug in RPC01-3102, it will be captured in the eCRF for RPC01-3102. All SAEs that occur within 90 days of the last dose of treatment with the investigational drug, whether or not considered related to the investigational drug, must also be reported. Any SAE that is ongoing when the patient completes the trial or discontinues from the trial will be followed by the Investigator until the event has resolved, stabilized, or returned to Baseline status.

Any AE considered serious by the Investigator or Sub-investigator or that meets serious criteria should be reported to the CRO's Pharmacovigilance group using the designated SAE reporting forms as well as eCRF forms and procedures. Data entry must be completed within 24 hours from the time the trial site personnel first learned of the event.

The SAE hotline contacts are as follows:

[contact]

[contact]

Email: [contact]

The initial report should be promptly followed by detailed, written reports, which will include copies of hospital case records, discharge summaries, autopsy reports, and other documents when requested and applicable. For unrelated cases, a full detailed case description may negate the need for additional hospital case records, discharge summaries, etc.

13.2.5.1 Reporting of Serious Adverse Events to Regulatory Authorities and Investigators

Investigators will be notified by the CRO of all SAEs that require prompt submission to their IRB or IEC. Investigators should provide written documentation of IRB/IEC notification for each report to the CRO. The CRO will ensure that all SAEs are reported to the appropriate Regulatory Authorities as required. Reporting of SAEs must comply with ICH E6, 4.11.1.

[figure not shown]
[figure not shown]
13.2.6 Adverse Events of Special Interest

[figure not shown]
Potential AEs that may be a consequence of S1P₁ modulation will be closely monitored during the trial. [REDACTED]

[REDACTED] The study team will perform routine safety reviews starting after the first patient is dosed with investigational product.

Special considerations regarding monitoring for these events are as follows: [REDACTED]

13.2.7 [REDACTED] Pandemic

[figure not shown]
[REDACTED] pandemic has been identified as a potential risk to clinical trial patients in general and may particularly affect individuals with underlying chronic diseases on immunomodulatory therapies. It is not known whether taking ozanimod increases the risk of [REDACTED] infection, or the duration or severity [REDACTED].

Evaluation and management of [REDACTED] infections arising during the course of the trial are left to the discretion and expertise of the investigator. For patients who exhibit symptoms consistent with [REDACTED], testing for [REDACTED] to inform decisions and clinical care during the study should follow local standard practice. The Sponsor advises the Investigator to consult the Medical Monitor.

Each study visit will include an assessment for AEs including [REDACTED] and other infections. In order to facilitate reporting of [REDACTED] events that occur during the study, all AEs and SAEs related to [REDACTED] should be reported from the time of consent until the final study visit.

Procedures related [REDACTED]

[REDACTED] and treatment (eg, intubation, dialysis) must be reported in the appropriate eCRF.

Administration of vaccinations must be reported along with dates of administration, vaccine name/trade name, location, and laterality in the appropriate eCRF. A separate logline should be entered for each vaccine administered.

13.2.8 Monitoring of Patients with Adverse Events, Serious Adverse Events, and Adverse Events of Special Interest

- Investigators must carefully monitor each patient for AEs. This includes clinical laboratory variables. Assessments must be made of the seriousness, severity, and relationship to the administration of the investigational drug. After the initial AE/SAE report, the Investigator is required to follow up proactively with each patient and provide further information to the CRO on the patient's condition. During the trial, all AE/SAEs should be followed up to resolution unless the event is considered by the Investigator to be unlikely to resolve due to the patient's underlying disease, or the patient is lost to follow-up. Safety reporting must comply with ICH E6, 4.11.

13.2.9 Overdose of Investigational Drug

An overdose is any dose of investigational drug given to a patient or taken by a patient that exceeds the dose described in the protocol. There is no information available regarding overdose with

RPC1063. Any overdose, with or without associated AEs, must be promptly reported to the CRO's Medical Monitor or other designated Drug Safety Center. Overdoses need to be recorded in the drug log in the eCRF; but only in the case of any AEs associated with the overdose should these be reported on relevant AE/SAE sections in the eCRF.

13.2.10 *Procedures in Case of Pregnancy*

If a urine pregnancy test is positive, the Investigator will instruct the patient to suspend further RPC1063 dosing. If the test was performed by the patient between scheduled visits, a follow-up appointment will be scheduled as soon as possible. A serum pregnancy test will be performed for confirmation.

Pregnancy in itself is not regarded as an AE unless there is a suspicion that an investigational drug may have interfered with the effectiveness of a contraceptive medication; however, the outcome of all pregnancies (spontaneous miscarriage, elective termination, normal birth, or congenital abnormality) must be followed up and documented even if the patient was discontinued from the trial. In cases of live birth, the infant will be followed for up to a year.

Male patients should also be instructed to notify the Investigator in the event that their female partner becomes pregnant. Attempts should be made to follow female partners of trial patients, if they should become pregnant. The Investigator must obtain informed consent from the pregnant partner of a trial patient prior to collecting data on her pregnancy and its outcome.

All reports of congenital abnormalities/birth defects are SAEs. Spontaneous miscarriages should also be reported and handled as SAEs. Elective abortions without complications should not be handled as AEs. All outcomes of pregnancy must be reported to the Sponsor and/or its designee. In cases of live birth, the infant will be followed for up to a year.

13.2.11 *Data Safety Monitoring Board*

An independent Data Safety Monitoring Board (DSMB) was charged with monitoring data from the trial as part of the ozanimod UC Phase 3 program, as well as general aspects of trial conduct. The DSMB scope, conduct, processes, and accountabilities are specified in a separate charter.

The committee met periodically during the trial (approximately 4 times each year) to review aggregate analyses by treatment group including but not limited to enrollment, treatment compliance, adherence to follow-up schedule, and safety data from the trial. The DSMB recommended to continue the study without modification and did not recommend modifying or stopping the trial early due to safety concerns based on data reviews.

As the maintenance period has been completed for the RPC01-3101 study, the DSMB will no longer meet to review data from the UC Phase 3 program. The internal team will continue to monitor the data from this open-label extension study.

13.4 Appropriateness of Measurements

The efficacy and safety assessments are standard assessments and deemed to be reliable, accurate, and relevant for this indication and patient population.

14 PLANNED STATISTICAL METHODS

14.1 Determination of Sample Size

As this is an open-label extension trial for patients who previously participated in a trial of RPC1063 in UC, there is no statistical basis for the sample size. It is anticipated that up to █ patients who participated in prior studies of RPC1063 in UC may be eligible for treatment in this trial.

14.2 Statistical Methods

14.2.1 General Considerations

All efficacy and safety data will be listed by patient. Baseline is defined as the last observed measurement prior to the Day █ receipt of investigational drug.

In general, descriptive summaries will be presented for the efficacy and safety variables collected. Continuous variables will be summarized using number of patients (n), mean, standard deviation (SD), minimum, median, and maximum. Categorical variables will be summarized using frequency counts and percentages.

14.2.2 Analysis Populations

All patients who receive at least one dose of investigational drug will comprise both the Intent-to-Treat (ITT) population and the Safety population. These populations will be used to summarize all efficacy and safety data, respectively.

14.3 Disposition, Demographics, and Baseline Characteristics

The number and percentage of patients in each population will be summarized. Patient disposition, including the number of patients screened, dosed, and not completing trial by reason for dropout will be summarized. Patient demographics will be summarized and will include age, sex, race, ethnicity, height, weight, and body mass index.

Baseline characteristics for each patient from their previous trial will be summarized and will include age at UC symptom onset, age at UC diagnosis, years since UC symptom onset, years since UC diagnosis, prior anti-tumor necrosis factor use, prior corticosteroid use, each component of the Mayo score, the complete Mayo score, the partial Mayo score, and the 9-Point Mayo score.

Compliance with investigational drug will be summarized and will include the number of patients estimated to be < 80% compliant, 80 to 100% compliant, > 100%, and > 120% compliant.

14.4 Efficacy

Due to the open-label nature of the trial and the lack of a control group, all data will be summarized, and no hypothesis testing will be performed. Each efficacy endpoint will be summarized and 95% confidence intervals around the estimates may also be presented. All efficacy data will be listed.

14.4.1 Handling Missing Data

For all proportion-based efficacy endpoints, patients with missing efficacy data will be considered non-responders.

For continuous efficacy endpoints, patients with missing data will have their last post-baseline value carried forward.

Observed-cases analyses will also be presented for all efficacy endpoints.

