Safety Monitoring/Follow-up: 
The safety of patients will be monitored by collection of treatment-emergent adverse events (TEAEs), serious adverse events (SAEs), TEAEs leading to discontinuation, and TEAEs of special interest, as well as, physical examination findings, vital signs measures, electrocardiograms (ECGs) findings, [REDACTED] results, [REDACTED] results, clinical laboratory test results (blood chemistry including liver transaminases, hematology). White blood cell (WBC) and [REDACTED] will be centrally monitored.
 
Patients entering the trial from the open-label period of RPC01-202 or from the open-label [REDACTED] of RPC01-3101 will continue to receive RPC1063/ozanimod HCl at 1 mg daily and no additional cardiac monitoring is required. All patients who enter this trial from a parent blinded trial or treatment period of RPC1063 [REDACTED] of RPC01-3101) will undergo [REDACTED]
 
Patients who discontinue from treatment for any reason, including lack of response and AE, even if alternative treatment is given, will be followed for 90 days for collection of safety data and for assessment of their disease status.
	

In the event that commercial ozanimod becomes available prior to end of the study, patients may discontinue and transition to the commercial product after discussion with the Investigator at his/her discretion. Patients who transition to commercial ozanimod prior to completing the study are not required to attend the Safety Follow-up (SFU) Visit after their [REDACTED] visit as long as commercial ozanimod is started within 14 days of discontinuation of study drug.

Patients who complete 5 years (Week 238) of treatment may transition to commercial RPC1063/ozanimod HCl if approved and available in their country. In countries where commercial ozanimod is not available, patients may be eligible for a country-specific support program where available (see [Section 8.3.6](#) for details).

Endoscopy:

All endoscopies will be recorded and read by a central reader.

Number of patients: Up to [REDACTED]

Diagnosis and main criteria for inclusion:

Inclusion Criteria:

Patients are eligible if they fulfill all of the following:

1. Previously participated in a trial of RPC1063 (eg, RPC01-3101 or completed at least 1 year of the open-label period of RPC01-202) and meet the criteria for participation in the open-label extension as outlined in the prior trial.
2. Females of childbearing potential (FCBP):

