7.2 Efficacy Endpoints

7.2.1 Definitions

Complete Mayo score: the sum of the RBS, SFS, PGA subscore, and the MES. Each subscore has a range of 0-3 points and the complete Mayo score has a range of 0-12 points

9-point Mayo score: the sum of the RBS, SFS, and the MES. The 9-point Mayo score has a range of 0-9 points

Partial Mayo score: the sum of the RBS, SFS, and the PGA subscore. The Partial Mayo score has a range of 0-9 points

Clinical Remission

Three-component Mayo: RBS = 0 and SFS \leq 1 (and a decrease of \geq 1 point from the baseline SFS) and MES \leq 1

Clinical Response

Three-component Mayo: A reduction from Baseline in the 9-point Mayo score of \geq 2 points and \geq 35%, and a reduction from Baseline in the RBS of \geq 1 point or an absolute RBS of \leq 1 point

Corticosteroid-free Remission: Clinical remission while off corticosteroids for \geq 12 weeks

Endoscopic Improvement: MES of \leq 1 point

Mucosal Healing: MES of \leq 1 point and a Geboes index score $<$ 2.0

Histologic Remission: Geboes index score $<$ 2.0

For statistical analysis purposes, clinical remission and clinical response will be calculated using the Three-component Mayo definition.

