9.2 Exclusion Criteria

Patients are not eligible for this trial if they fulfill any of the following:

Exclusions Related to Medications:

- 1) Have received any of the following therapies since the first dose of investigational drug in the prior RPC1063 trial:
 - Treatment with a biologic agent
 - Treatment with an investigational agent other than RPC1063
 - Treatment with D-penicillamine, leflunomide, thalidomide, natalizumab, fingolimod, etrasimod, or tofacitinib
 - Treatment with lymphocyte-depleting therapies (eg, Campath, anti-CD4, cladribine, rituximab, ocrelizumab, cyclophosphamide, mitoxantrone, total body irradiation, bone marrow transplantation, alemtuzumab, daclizumab)
 - Treatment with a live vaccine or live attenuated vaccine within 4 weeks prior to Visit █ of this trial
- 2) Are currently receiving or require initiation of any of the following therapies:
 - Treatment with corticosteroids at a dose that exceeds the prednisone equivalent of 40 mg
 - Treatment with immunosuppressive agents (eg, azathioprine, 6-MP, or methotrexate)
 - Chronic non-steroidal anti-inflammatory drug (NSAID) use (Note: occasional use of NSAIDs and acetaminophen [eg, headache, arthritis, myalgias, or menstrual cramps] and aspirin up to 325 mg/day is permitted)
 - Treatment with Class Ia or Class III anti-arrhythmic drugs or treatment with two or more agents in combination known to prolong PR interval
- 3) Are receiving treatment with any of the following drugs or interventions within the corresponding timeframe:
 - At Day █
 - CYP2C8 inhibitors (eg, gemfibrozil or clopidogrel) or inducers (eg, rifampicin)
 - Two weeks prior to Day █
 - Monoamine oxidase inhibitors (eg, selegiline, phenelzine)
- 4) Are receiving treatment with breast cancer resistance protein (BCRP) inhibitors (eg, cyclosporine, eltrombopag)

Exclusions Related to General Health:

- 5) Pregnancy, lactation, or a positive serum beta human chorionic gonadotropin (hCG)
- 6) Clinically relevant hepatic, neurological, pulmonary, ophthalmological, endocrine, psychiatric or other major systemic disease making implementation of the protocol or interpretation of the trial difficult or that would put the patient at risk by participating in the trial or that would have required a patient to discontinue treatment in previous RPC1063 trial
- 7) Clinically relevant cardiovascular conditions, including history or presence of recent myocardial infarction, unstable angina, stroke, transient ischemic attack,

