10.5.1 Allowed Medications

All prior medications (including over-the-counter medications) administered [REDACTED] prior to the date of informed consent and any concomitant therapy administered to the patient during the course of the trial (including any ongoing medications at the end of the parent study and new medication started after the completion of the parent study or medications that were initiated in

the prior study) until [REDACTED] after the final dose of investigational drug will be recorded. Any medication that is considered necessary for the patient's health and that is not expected to interfere with the evaluation of or interact with investigational drug may be continued during the trial.

10.5.2 Concomitant Medications Prohibited Through [REDACTED] After Investigational Drug Discontinuation

The following medications cannot be used during the trial through [REDACTED] after investigational drug discontinuation:

- Treatment with Class Ia or Class III anti-arrhythmic drugs [REDACTED] or treatment with 2 or more agents in combination known to prolong PR interval (eg, combination of a beta blocker and calcium channel blocker such as verapamil) are prohibited during the study unless approved by the Sponsor's representative.
- Marketed biologic therapies such as abatacept, infliximab, etanercept, adalimumab, golimumab, certolizumab, anakinra, rituximab, vedolizumab, and ustekinumab
- Immunomodulatory agents (eg, etrasimod, natalizumab, fingolimod, or tofacitinib)
- Immunosuppressive agents (eg, AZA, 6-MP, cyclosporine, methotrexate, oral cyclosporine, tacrolimus, sirolimus or MMF) or other antineoplastic therapies or immune-modulating therapies
- Any investigational treatment other than the investigational drug specified in this trial
- Live vaccines or live attenuated vaccines
- Intravenous immunoglobulin (IV-Ig) or plasmapheresis
- D-penicillamine, leflunomide, or thalidomide
- Breast cancer resistance protein (BCRP) inhibitors (eg, cyclosporine, eltrombopag)
- Monoamine oxidase inhibitors (eg, selegiline, phenelzine)
- CYP2C8 inducers (eg, rifampicin). For patients who are currently enrolled and are receiving monoamine oxidase inhibitors or CYP2C8 inducers, an individual safety assessment will be conducted and, if indicated, either the concomitant medication will be discontinued and the patient will continue in the study or investigational drug will be discontinued and the patient will be withdrawn from the study.

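### Apart from corticosteroid-free remission, no binary efficacy endpoint accounts for corticosteroids started or increased, or prohibited UC therapy taken, by a patient who stays on study

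*Combined protocol and SAP*

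**What the plan says.** Section 14.4.1 has three provisions.

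- Binary endpoints: "For all proportion-based efficacy endpoints, patients with missing efficacy data will be considered non-responders".
- Continuous endpoints: "For continuous efficacy endpoints, patients with missing data will have their last post-baseline value carried forward".
- Both types: "Observed-cases analyses will also be presented for all efficacy endpoints".

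None of them mentions concomitant therapy.

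The definitions in Section 7.2.1 rest on scores. Endoscopic improvement, for example, reads "Endoscopic Improvement: MES of" at most 1 point. The one definition with a therapy condition is corticosteroid-free remission: "Clinical remission while off corticosteroids for" at least 12 weeks.

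On therapy itself, Section 9.2 bars entry for "Treatment with corticosteroids at a dose that exceeds the prednisone equivalent of 40 mg", so lower doses are compatible with enrolment. Section 10.5.2 opens its list with "The following medications cannot be used during the trial through" a redacted time after stopping the drug. It names biologics, immunomodulators and immunosuppressants. Corticosteroids do not appear in its visible text, nor in that of Section 10.5.3.

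**The concern.** Section 6.1 describes corticosteroids as effective at inducing remission in UC. They can therefore produce the outcomes being counted. A patient who flares on ozanimod, is given corticosteroids and scores well at the next assessment is a success for response, endoscopic improvement, mucosal healing and histologic remission. The same patient is also a success for clinical remission. Only corticosteroid-free remission would exclude that patient.

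The flare may leave no other trace in the summaries. Section 13.2.1 does not record non-serious UC relapse as an adverse event, on the ground that relapse is followed through the trial endpoints. The visible endpoint list in Section 7.2.2 has no relapse endpoint.

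The trial has no control arm and, under Section 14.4, no hypothesis tests. Its efficacy product is the estimated proportions and their optional confidence intervals, and Section 6.3 says continued treatment is meant to give durability data. No between-arm contrast exists to cancel success that owes something to added therapy.

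**Working it through.** **The plan's own figure.** There is none to reproduce. Section 14.1 states no statistical basis for the sample size, and Section 14.4 excludes testing.

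**Step 1: which endpoints carry a therapy condition (Section 7.2.1)**

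| Endpoint | Condition on corticosteroids | Condition on other UC therapy |
|---|---|---|
| Clinical response | none | none |
| Clinical remission | none | none |
| Endoscopic improvement | none | none |
| Mucosal healing | none | none |
| Histologic remission | none | none |
| Corticosteroid-free remission | off for at least 12 weeks | none |

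The Section 7.2.2 endpoint in patients with prior anti-TNF therapy reuses response, remission and endoscopic improvement, so it inherits the gap.

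**Step 2: which therapies can coexist with an observed score**

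- *Corticosteroids on study:* allowed at entry up to the Section 9.2 limit and absent from the visible prohibited lists. A corticosteroid-free endpoint also presupposes that some patients are on them at assessment.
- *Prohibited UC therapy in a patient who stays on study:* a deviation under Section 10.5.2, but no rule makes the patient a non-responder.
- *Alternative therapy after stopping the drug:* Section 9.4 withdraws patients who stop the drug and places alternative UC treatment after that. Later scheduled visits are missing and already count as failures.

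**Step 3: effect on a binary proportion**

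Let q be the share of the ITT population that has the therapy of interest before the visit and is still assessed. Let r be the share of those patients who meet the endpoint. Then:

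proportion under the present rule − proportion under a treatment-failure rule = q × r

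This is never negative. The documents give neither q nor r, so the values below are assumptions.

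| q | r | q × r |
|---|---|---|
| 5% | 40% | 0.05 × 0.40 = 2.0 points |
| 10% | 55% | 0.10 × 0.55 = 5.5 points |
| 15% | 70% | 0.15 × 0.70 = 10.5 points |

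A wider range gives 0.05 × 0.30 = 1.5 points to 0.20 × 0.70 = 14 points.

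**Step 4: from difference to misattribution**

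If a share r0 of the affected patients would have met the endpoint without the added therapy, the misattributed part is q × (r − r0). With r0 at or above zero, this is at most q × r.

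**Step 5: continuous endpoints**

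The last-value rule can carry a Mayo score taken under added corticosteroids to later visits, and observed cases use such scores directly. The likely direction is towards apparent improvement, but no inequality like that in Step 3 guarantees it.

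**The case against.** **The permission is inferred.** No visible text expressly allows starting or raising corticosteroids. Section 10.5.1 permits necessary medication only if it should not disturb the evaluation of the study drug or interact with it, and rescue corticosteroids might fall outside that. The List of Tables also shows a redacted table on the page where Section 10.5.2 falls. This limits certainty. It does not close the gap: even if such use were a deviation, 14.4.1 would still count the patient by score.

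**A separate SAP may hold the rule.** The summary of changes from Version 2.0 to 3.0 defers Mayo calculation details to a Statistical Analysis Plan, and no separate SAP text is in the document. A rule there cannot be excluded. If one exists, 14.4.1 should cite it.

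**The choice is legitimate.** Summarising outcomes regardless of concomitant therapy is a recognised strategy in a descriptive trial, and corticosteroid-free remission is paired with it. This stands as a reason to add an analysis rather than replace one. The pairing protects remission only, and only against corticosteroids.

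**Stronger readings the documents do not support.**

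- A reader might infer that success under any later UC therapy is credited to ozanimod. For therapy begun after stopping the drug this is largely wrong, as Step 2 of the working shows. The Synopsis does say such patients, "even if alternative treatment is given, will be followed for 90 days for collection of safety data" and disease status. But Section 12.3 collects the symptom diary only to a redacted visit that is probably not the 90-day visit, and the Table 2 cells are missing. It is not shown that these values enter any efficacy summary.
- A reader might infer that the reported rates are biased upward overall. That holds only relative to a treatment-failure rule. Some treated patients would have succeeded anyway. Patients who move to commercial ozanimod while doing well become missing and count as failures, which pulls the other way.

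**Conclusion.** The point holds for therapy taken while the patient remains on study, mainly corticosteroids and secondarily prohibited UC drugs. As written, such a patient is a success on every binary endpoint except corticosteroid-free remission, and a prohibited non-steroid therapy does not bar even that one.

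The direction against a treatment-failure rule is certain for binary endpoints. The size is not known. The 2 to 10.5 points rest entirely on the assumed 5-15% and 40-70%, and they are an upper bound on what is wrongly credited to the drug. The net direction of error in the reported rates is not established.

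No error rate or power is affected. What is affected is how far an uncontrolled long-term proportion can be read as durability on ozanimod. The conclusion assumes that the redacted text and any separate SAP contain no treatment-failure rule.

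**What to change.** Add to Section 14.4.1, for each proportion-based endpoint, a second analysis presented beside the present one. In it a patient is a non-responder if, at any time in the 12 weeks before the assessment, he or she was taking either of these:

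- corticosteroids for UC that were newly started since entry to this trial or were above the entry dose, whenever that use began; or
- a UC therapy prohibited by the protocol.

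The 12 weeks match the plan's own corticosteroid-free window. Defining the rule by use within the window, rather than by start date, matters: corticosteroids begun 13 weeks earlier and still being taken would otherwise escape.

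For the continuous endpoints, add a version of the last-value and observed-case summaries that leaves out values taken under such therapy.

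No new data are needed. Section 10.5 already requires dose, dates and reason for each concomitant medication. Keeping the present rule preserves comparability with the interim analyses in Section 14.6 and lets readers see how much success coincides with added therapy. The cost is one more set of tables, the derivation behind them, and lower reported rates under the added rule. Nothing changes in treatment or visits.
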